# 6. GENERAL ASPECTS FOR STATISTICAL ANALYSIS

#### **6.1. GENERAL METHODS**

Unless otherwise specified, for numeric data, descriptive statistics will include the number of subjects with data to be summarized (n), mean, standard deviation (SD), median, minimum (min), and maximum (max). The same number of decimal places as in the raw data will be presented when reporting min and max, 1 more decimal place than in the raw data will be presented when reporting mean and median, and 2 more decimal places than in the raw data will be presented when reporting SD. If the raw data have 3 decimals or more, 3 decimals will be presented for mean, median, min and max, and SD.

All categorical/qualitative data will be presented using absolute or relative frequency counts and percentages. All percentages will be presented with 1 decimal point. Percentages equal to 100 will be presented as 100% and percentages will not be presented for zero frequencies but the categories whose counts are zero will be displayed for the sake of completeness.

P-value > 0.9999 will be present as '> 0.9999' and p-value < 0.0001 will be presented as '< 0.0001'.

All analyses and summary outputs will be generated by treatment group (Placebo, SYN-010 21 mg, SYN-010 42 mg) using SAS® version 9.3 (or higher).

Data collected in this study will be presented in by-subject listings.

#### 6.2. BASELINE AND STUDY DAY DEFINITIONS

Baseline definition will vary upon the data/variables for summaries/analyses.

Table 1: Baseline Definitions

Data/Variables	Baseline Definition
Laboratory, vital signs, and ECG	The last non-missing value prior to the first dose of the study drug
Breath CH 4 AUC measurement	AUC of breath CH 4 measurements collected during lactulose breath test performed at Screening after an overnight fast
Singe-point breath CH 4 measurement	A single-point breath CH 4 measurement collected at Randomization after an overnight fast
Weekly average score for worst abdominal pain in the past 24 hours	(Sum of daily pain scores) / (number of days with pain score assessment during the 7 days prior to the first dose of study drug)
Stool frequency of CSBMs per week/Weekly average number of CSBMs	7 x (sum of daily number of CSBMs) / (number of days with CSBM assessment

	during the 7 days prior to the first dose of study drug)
Stool frequency of SBMs per week/Weekly average number of SBMs	7 x (sum of daily number of SBMs) / (number of days with SBM assessment during the 7 days prior to the first dose of study drug.
Weekly average of bloating score	Sum of daily bloating scores / (number of days with bloating score assessments during 7 days prior to the first dose of study drug)
Weekly average of straining score	Sum of daily straining scores / (number of days with straining score assessments during 7 days prior to the first dose of study drug)
Adequate Relief	The last non-missing value prior to the first dose of the study drug
Weekly stool consistency score (BSFS)	Sum of (i $\times$ number of type i stools) / total number of stools during 7 days prior to the first dose of study drug, where stool consistency i = 1, 2,7
EQ-5D-5L score	The last non-missing value prior to the first dose of the study drug

Study day will be defined as follows:

- The first dose of study drug is designated as Day 1.
- For visit days after Day 1, study day = visit date Day 1 date + 1.
- For visit days prior to Day 1, study day = visit date Day 1 date. Thus, study days for screening visit are negative numbers. There is no "Day 0".

#### 6.3. VISIT WINDOWS

The unscheduled or early termination (ET) visit will be mapped to a scheduled visit for analysis using the date of collection/assessment as a basis to determine study day and then study day will be mapped to the intended visit. The table below contains the analysis visit windows.

Once analysis visit windows get assigned, all visits, including scheduled visits, unscheduled visits, and early termination visits will be eligible for being flagged as the "analyzed record" within the analysis visit window, a subject's individual analysis visit window could potentially contain more than one visit. In the event of multiple visits falling within an analysis visit window or in case of a tie, the following rules will be used in sequence to determine the "analyzed record" for the analysis visit window:

• If there is a scheduled visit/week for the analysis visit window, then the scheduled visit/week data will be used.

- If there is no scheduled visit/week for the analysis visit window, the data closest to the scheduled day will be used.
- If there is no scheduled visit/week for the analysis visit window and there is a tie between the data in the number of days before and after the scheduled day, the later data will be used.

The data not flagged as the "analysed record" will also be listed in subject listings.

Table 2: Definitions of Analysis Windows

Study Day Window	Scheduled day	Scheduled Visit/Week
Days (-17) to (-1)	Day -1	Visit 1/Screening
Day 1	Day 1	Visit 2/Randomization
Day 2 - 42	Day 28	Visit 3/Day 28
Day 43 – 70	Day 56	Visit 4/Day 56
Day 71 - 84	Day 84	Visit 5/Day 84
Day 85 - 86	Day 85	End-of-Study Contact

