# 9.4. LABORATORY EVALUATIONS

If a continuous laboratory value is reported as either below or above the limits of quantification, the qualifiers should be dropped and the numeric value used in the analysis (e.g., "< 3" should be "3" and "> 200" should be "200").

The observed data at each time point and change from baseline at each post-baseline time point in hematology, serum chemistry and quantitative urinalysis test results will be summarized by treatment group.

For hematology, serum chemistry, lipid, cytokine, and creatine phosphokinase, normal ranges for each parameter will be used to categorize the test result as low (value lower than the lower limit), normal (value within the normal range), or high (value higher than the upper limit). Frequency counts and percentages will be presented over time by treatment groups for these categorical data. In addition, shifts from baseline to each post-baseline time point for each parameter will be summarized by treatment group.

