# 9.6. ECG

Observed data at each time point and the change from baseline at Week 12 in ECG parameters (HR, RR, PR, QRS, and QTcF) will be summarized by treatment group.

The number and percentage of subjects with QT and QT corrected with Fridericia's formula (QTcF) values falling into the following categories at Week 12 will be summarized by treatment group:

- Change from baseline of 30 60 msec in QT and QTcF.
- Change from baseline of > 60 msec in QT and QTcF
- Week 12 value > 450 and baseline <= 450 msec in QT and QTcF
- Week 12 value > 500 and baseline <= 500 msec in QT and QTcF

QTcF (msec) is calculated as: QT (msec)/  $RR^{1/3}$ , where RR = 60 / heart rate (bpm).

The number and percentage of subjects with other clinically significant ECG findings and rhythm findings will also be summarized at Week 12 by treatment group.

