## 9.7. RESCUE MEDICATION

The number and percentage of subjects using protocol-specified rescue medication at any time post-baseline will be summarized by treatment.

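### SAP 9.6 counts QT/QTcF categories and ECG findings at Week 12 only, so an early-termination ECG before Day 71 cannot enter those counts

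*SAP*

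**What the plan says.** **Mapping of visits (SAP 6.3 and Table 2).** The rule is date-based: "The unscheduled or early termination (ET) visit will be mapped to a scheduled visit for analysis using the date of collection/assessment as a basis". Table 2 gives Days 2-42 to Visit 3, Days 43-70 to Visit 4 and Days 71-84 to Visit 5. ECG is not excepted. When several records fall in one window, "If there is a scheduled visit/week for the analysis visit window, then the scheduled visit/week data will be used"; the others are only listed.

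**ECG summaries (SAP 9.6).** Three outputs are tied to Week 12:
- the parameter summary: "Observed data at each time point and the change from baseline at Week 12 in ECG parameters";
- the QT and QTcF category counts: "values falling into the following categories at Week 12 will be summarized by treatment group", one category being "Week 12 value > 500 and baseline <= 500 msec in QT and QTcF";
- the remaining findings: "other clinically significant ECG findings and rhythm findings will also be summarized at Week 12 by treatment group".

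**When ECGs are taken (Protocol 9.1 Table 1 and 9.3.5).** ECGs are planned at Screening and at Visit 5. The Visit 5 column in Table 1 covers Day 84 or ET, so a patient who stops early has an ECG at the ET visit.

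**Withdrawal criteria (Protocol 9.3.13).** These include a Fridericia-corrected QTc above 500 ms, a rise of more than 60 ms from baseline, and certain new arrhythmias or ischemic signs.

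**The concern.** The two SAP sections work against each other. The ET ECG replaces the Visit 5 ECG for a patient who stops early, but the date rule moves it to a visit for which SAP 9.6 plans no change from baseline, no category count and no count of findings.

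The patients affected are not a random subset. The SAP categories for a value above 500 ms and a rise above 60 ms use the same thresholds as two of the withdrawal criteria in Protocol 9.3.13. A patient withdrawn before Day 71 for such a reading would be absent from the table that is meant to count it. At stake is whether the QT/QTcF outlier table is complete. No efficacy result depends on it.

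**Working it through.** The plan has no figure of its own to reproduce here. The check applies SAP Table 2 to each study day and compares the result with the time points in SAP 9.6.

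**1. Where an ET or unscheduled ECG goes**

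| Study days | Number of days | Assigned to | In the Week 12 counts? |
|---|---|---|---|
| 2-42 | 42 - 2 + 1 = 41 | Visit 3 | No |
| 43-70 | 70 - 43 + 1 = 28 | Visit 4 | No |
| 71-84 | 84 - 71 + 1 = 14 | Visit 5 | Yes, if it is the analyzed record |

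Days 2 to 84 are 41 + 28 + 14 = 83 days. On 41 + 28 = 69 of them (69/83 = 83%) the ECG falls outside the counts. This is a share of days, not of patients.

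**2. Whether another rule brings these ECGs back**
- SAP 9 rules out imputing missing safety data, so nothing carries an earlier ECG forward to Week 12.
- SAP 9.6 has no worst-value, last-value or any-time count.
- SAP 5.1 names Week 12 and early termination as separate occasions for the EQ-5D-5L. SAP 9.6 names Week 12 alone.

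**3. Days 71-84**

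An ET ECG in this window can be the Week 12 record. An unscheduled ECG is displaced if a scheduled Visit 5 record exists. This precedence rule is general and acts on laboratory and vital-sign records in the same way.

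**4. How many patients**

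Protocol 6.6 reports 53 randomized, of whom 49 completed and 4 withdrew or terminated early. Their stopping days are not given, nor whether an ET ECG was done. The number of ET ECGs affected so far is therefore 0 to 4, and 4/53 = 7.5% at most.

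**5. What one uncounted case would do**

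Protocol 8.1 uses blocks of 6 at 1:1:1. Assuming one list used in order, 53 = 8 × 6 + 5. Eight full blocks give 16 per group and the last, incomplete block gives 2 + 2 + 1, so the groups are 18, 18 and 17. Assuming all treated patients form the denominator (SAP 9.6 does not state it) and all those randomized were treated, one uncounted case changes a category from 0% to:
- 1/18 = 5.6% or 1/17 = 5.9% in the current groups;
- 1/50 = 2.0% in a full group of 50.

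These figures show sensitivity to one hypothetical case. They do not estimate how many cases are missed.

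**The case against.** **Much of the information survives.** SAP 9.6 summarizes observed ECG values at each time point, and SAP 6.1 includes the maximum. An early QTcF above 500 ms, if it is the analyzed record, would show as the Visit 3 or Visit 4 maximum of its group. The patient also appears in listings, in disposition by reason (SAP 7.1) and, if the event is recorded as an adverse event, in the TEAE tables (SAP 9.3). This stands and limits the consequence. None of these outputs counts patients by QTcF category, and the maximum does not show a rise from baseline.

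**Week 12 may simply mean the Visit 5 column of the protocol, which includes ET.** That may be the intention, but SAP 6.3 assigns ET visits by date and SAP 9.6 does not mention ET.

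**Few ECGs before Day 71 are likely.** Table 1 marks physical examination and creatine kinase as symptom-directed at some visits, but not ECG. A QTc withdrawal before Day 71 would need an unscheduled or ET ECG, and the documents give no count of unscheduled ECGs. This stands, so the size above is given for ET ECGs only.

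**ECG differs from the data with broader summaries.** SAP 9.4 reports "change from baseline at each post-baseline time point in hematology, serum chemistry", and SAP 9.7 counts "subjects using protocol-specified rescue medication at any time post-baseline". Laboratory tests have several planned visits and rescue use comes from a daily diary, whereas ECG has one planned post-dose time. That explains the Week 12 wording but does not close the gap. A reader might also infer that laboratory and vital-sign summaries are free of the problem. They are not restricted to Week 12, but the precedence rule can displace unscheduled records there too.

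**Conclusion.** The gap is real and minor. Under the rules as written, an ET ECG before Day 71 cannot enter the change-from-baseline summary, the QT/QTcF categories or the count of ECG findings. At most 4 of 53 patients so far could have such an ECG. The bound assumes that every early stopper stopped before Day 71 and had an ECG.

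Three stronger readings are not supported:
- **That QTc outliers have been missed.** The documents report no such event. The bound counts ECGs that could be left out, not outliers.
- **That early ECGs are lost from the analysis.** They remain in the observed summaries and the listings.
- **That completers seen after Day 84 also drop out of the Week 12 table.** Protocol Version 8.0 allows Visit 5 on Days 79-89, while SAP Table 2 closes that window at Day 84 and gives Days 85-86 to the end-of-study contact. However, SAP 6.3 can be read as letting scheduled visits keep their label, and the SAP is written to Protocol Version 3.0, whose window is not in the documents. This is a matter for reconciliation only.

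**What to change.** In SAP 9.6, add a QT/QTcF category count and an ECG-finding count based on any post-baseline ECG, including ET and unscheduled ones. Place them beside the Week 12 summary under their own label, and state the denominator for both sets.

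The cost is one or two sentences and one extra table column, with no new data. The drawback is that the added counts mix exposure durations and may include ECGs taken after the last dose, which is why they should supplement the Week 12 summary and not carry its label.

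A narrower choice is to define the time point in SAP 9.6 as Week 12 or ET. That would bring in the ET ECGs but not unscheduled ones, and it would put different exposure durations under one heading.

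As a note only: when SAP 6.3 is next edited, say whether scheduled visits keep their visit label, and reconcile Table 2 with the Visit 5 and end-of-study windows of the current protocol.

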4.3 Exploratory

Date: June 30, 2020

For SYN-010 relative to placebo:

- Proportion of patients with adequate relief²⁷.
- Change from baseline for SYN-010 in patient reported outcomes (PRO) using validated questionnaires in the REDCap system.
- Breath gas area-under-the-curve (AUC) (methane, hydrogen, and hydrogen sulfide) on lactulose breath test at EOS compared to Screening.
- Spot breath tests at Randomization, Day 28, and Day 56.
- Comparison of serum cytokine levels at baseline and EOS measuring for potential immune or inflammatory signals to include the key cytokines of the Th1/Th2/Th17 pathways: IL-2, IL-4, IL-5, IL-9, IL-10, IL-13, IL-17, GM-CSF and IFN-γ. Plus TNF-α, IL-12, IL-6, the two chemokines IL-8 and MCP-1, and the gut cytokine IL-25.
- Microbiome measurements in stool of bacteria (16S rRNA) and methanogens (qPCR).

5. Study design and investigational plan

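### SAP Table 2 closes the Visit 5 window on Day 84, the protocol allows Visit 5 up to Day 89, and no SAP rule says that an on-time scheduled visit keeps its label

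*SAP*

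**What the plan says.** Protocol 9.1, Table 1 schedules Visits 3, 4 and 5 on Days 28, 56 and 84 (or early termination for Visit 5), each ±5 days, and the End-of-Study call or visit on Day 85, +1 day.

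SAP 6.3, Table 2 has these rows for the end of the study (day window, target day, visit): "Day 43 – 70 Day 56 Visit 4/Day 56", then "Day 71 - 84 Day 84 Visit 5/Day 84", then "Day 85 - 86 Day 85 End-of-Study Contact". There is no later row.

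Three statements in SAP 6.3 govern how the table is used:
- Date mapping: "The unscheduled or early termination (ET) visit will be mapped to a scheduled visit for analysis using the date of collection/assessment". Scheduled visits are not named here.
- Eligibility: "Once analysis visit windows get assigned, all visits, including scheduled visits, unscheduled visits, and early termination visits will be eligible for being flagged" as the record analysed within a window.
- Selection within a window: "If there is a scheduled visit/week for the analysis visit window, then the scheduled visit/week data will be used".

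SAP section 2 states that the plan is based on Protocol Version 3.0. The protocol supplied is Version 8.0.

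**The concern.** Visit 5 is the only clinic visit whose analysis window stops on its target day. A patient who attends one to five days late, as the protocol allows, falls outside it. Read by study day, the table would either label that visit as the End-of-Study contact or leave it with no analysis visit.

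For several measures Visit 5 is the only scheduled post-baseline collection, so losing the label removes the patient from the comparison. One of these is the lactulose breath AUC. Protocol 4.3 describes its comparison as "on lactulose breath test at EOS compared to Screening", although Table 1 places the test at Visit 5. This double use of the end-of-study label makes a Day 85-86 misassignment easier to overlook. SAP 9.6 specifies the ECG change summaries at Week 12 only, so an ECG without that label drops out of them.

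**Working it through.** **1. Reproduce the bounds in Table 2.** The lower bounds follow from midpoints between target days: (28 + 56)/2 = 42, so Visit 4 starts on Day 43; (56 + 84)/2 = 70, so Visit 5 starts on Day 71. The upper bound of Visit 5 does not reproduce from the protocol: 84 + 5 = 89, whereas Table 2 has 84, the target day itself.

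**2. Map each allowed day to Table 2** (Day 1 = first dose, SAP 6.2).

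| Visit | Allowed days | Table 2 window | Own window | End-of-Study | No window |
|---|---|---|---|---|---|
| 3 | 23-33 | 2-42 | 11 of 11 | 0 | 0 |
| 4 | 51-61 | 43-70 | 11 of 11 | 0 | 0 |
| 5 | 79-89 | 71-84 | 6 of 11 (79-84) | 2 of 11 (85-86) | 3 of 11 (87-89) |

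**3. End-of-Study row.** Protocol 5.3 puts the contact 24 to 48 hours after Week 12. If it is timed from an actual Visit 5 on Day 89 (an assumption), it falls on Days 90-91, also outside Table 2.

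**4. Which data are exposed** (Protocol Table 1).
- Visit 5 is the only scheduled post-baseline collection: lactulose breath test, 12-lead ECG, hematology, lipid panel. EQ-5D-5L is a possible addition; it is entered in REDCap at Week 12, so its date need not be the clinic date.
- Only the Week 12 record is exposed: chemistry, cytokines, vital signs.
- Not exposed: the primary endpoint and the weekly diary endpoints, which use diary weeks. The stool sample is due in the week up to and including Day 84 (Table 1, footnote 12).

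**5. Possible size.** The documents give no distribution of visit days. The illustrations below restrict Visit 5 to Days 79-89, with days either equally likely or weighted by a normal density centred on Day 84. If a fraction f is lost equally in each arm, the standard error is multiplied by √(1/(1 − f)).

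| Assumed spread | Days 85-86 | Days 87-89 | SE factor, Days 87-89 lost | SE factor, Days 85-89 lost |
|---|---|---|---|---|
| Uniform | 2/11 = 0.182 | 3/11 = 0.273 | √(1/0.727) = 1.17 | √(1/0.545) = 1.35 |
| Normal, SD 2.5 days | 0.270 | 0.148 | √(1/0.852) = 1.08 | √(1/0.582) = 1.31 |
| Normal, SD 1.5 days | 0.322 | 0.045 | √(1/0.955) = 1.02 | √(1/0.633) = 1.26 |

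These factors apply only if Table 2 is used by study day for scheduled visits. Under nominal labels each factor is 1.

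**The case against.** A reader might infer that completers' data will certainly be lost. The documents do not support that. The date-mapping sentence covers only unscheduled and early-termination visits, and nothing says that a scheduled visit is relabelled. SAP 5.1 and 9.6 also name the breath test, EQ-5D-5L and ECG by Week 12 visit, which fits nominal labels. On that reading a Visit 5 on Day 87 stays Visit 5. This part of the objection stands: loss is conditional.

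It does not settle the matter. The eligibility sentence includes scheduled visits but places them within the day windows, the priority rule works one window at a time, and no sentence preserves the label of a scheduled visit outside its row. Two programmers could build different Week 12 datasets from the same text.

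A reader might also infer that close to half the patients are at risk, or that standard errors rise by a third. Those figures come from assumed spreads and from counting Days 85-86 as lost. Records on those days would be relabelled, not deleted, and they would be conspicuous because Table 1 schedules no breath test, ECG or routine laboratory test at the End-of-Study contact. Records not chosen for analysis are still listed.

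The importance is limited too. Breath AUC is exploratory, single-point breath methane is also measured on Days 28 and 56, and safety summaries are descriptive (SAP section 9).

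Finally, it cannot be said that the SAP contradicted the protocol it was written for. Version 3.0 was not supplied, and its Visit 5 window is unknown.

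**Conclusion.** The mismatch is a matter of record: against Protocol Version 8.0, the Visit 5 row of SAP Table 2 leaves out 5 of the 11 allowed days, while the Visit 3 and Visit 4 rows leave out none. Misassignment follows only if the table is applied to scheduled visits by study day. The eligibility sentence implies this, but the date-mapping sentence leaves room for the opposite. The proportion of patients involved is unknown. It could be counted without unblinding from the Visit 5 dates of the 49 patients reported as completers in Protocol 6.6.

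This should be corrected before the analysis datasets are built. The trial's main efficacy conclusion does not depend on it.

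**What to change.** 1. In SAP 6.3, state that scheduled visits, including Visit 5 and the End-of-Study contact, keep their nominal visit label, and that Table 2 places only unscheduled and early-termination records.
2. In Table 2, extend the Visit 5 row to Days 71-89 so that it contains the protocol window. Mark the End-of-Study row as assigned by label, so that Days 85-86 do not belong to two rows. Unscheduled records on Days 85-89 could then map to Visit 5, but the existing priority rule uses them only when no scheduled Visit 5 record exists.
3. Update the SAP's protocol reference and check Table 2 against the current schedule.
4. Optionally, repeat the breath AUC comparison without tests taken after dosing ended, with the cutoff specified by the sponsor in advance.

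The cost is one sentence, two table rows and one optional sensitivity analysis. No visit or procedure changes. The small downside is that a few measurements taken shortly after the last dose enter the Week 12 analysis; for breath AUC, item 4 shows their effect.

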Clinical studies with the commercially-available cholesterol-lowering lovastatin formulation Mevacor[®] (Merck) also found persistent increases (to more than 3 times the upper limit of normal) in serum transaminases occurred in 1.9% of adult patients who received lovastatin for at least one year in early clinical trials. When the drug was interrupted or discontinued in these patients, the transaminase levels usually fell slowly to pretreatment levels. The increases usually appeared 3 to 12 months after the start of therapy with lovastatin and were not associated with jaundice or other clinical signs or symptoms. SYN-010 is designed to limit systemic exposure to lovastatin species and SYN-010 21 mg and 42 mg doses did not cause clinically meaningful or persistent alterations to serum transaminase levels in Phase 1 or Phase 2a clinical trials.

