9.3.6 Blood draw

Blood will be drawn by a trained research nurse and collected for hematology, clinical chemistry, lipid, cytokine, and creatine phosphokinase. Laboratory analyses will be performed in the central clinical laboratory and MAST research laboratory at Cedars-Sinai Medical Center. Reference ranges will be supplied by the clinical laboratory and used by the investigator to assess the laboratory results for clinical significance and pathological changes. Blood samples will be used for serum pregnancy tests in women of childbearing potential.

Clinical chemistry (CMP) will be assessed on Visits 1 (Screening Visit), 2, 3, and 5. Creatine kinase (CK) will be assessed during Visit 1, however may be assessed as needed during the remaining study visits as indicated by the development of symptoms suggestive of myopathy and/or rhabdomyolysis.

Blood will be drawn during all visits except Visit 4 and the End-of-Study Call/Visit; however, blood may be drawn on Visit 4 and/or the End-of-Study Call/Visit as dictated by occurrence of subject symptom or adverse events.

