9.3.13 Further safety

Individual subject stopping criteria: If any subject demonstrates (i) clinical signs of potential serious liver injury, hepatotoxicity, and/or hyperbilirubinemia jaundice, or (ii) myopathy/rhabdomyolysis with or without acute renal failure secondary to myoglobinuria, or (iii) a hypersensitivity reaction determined by the investigator to be associated with treatment, that subject should be withdrawn from therapy.

An increase in serum aminotransferases to > 3x ULN will be followed by repeat testing within 48 to 72 hours to confirm the abnormality and determine whether they are increasing or decreasing. If an abnormality develops during the course of the study that meets any of the following criteria, the subject should be withdrawn:

- ALT or AST > 8x ULN;
- ALT or AST > 5x ULN for more than 2 weeks;
- ALT or AST > 3x ULN and (total bilirubin > 2x ULN or INR > 1.5); or
- ALT or AST > 3x ULN with the appearance of fatigue, nausea, vomiting, right upper quadrant pain or tenderness, fever, rash, and/or eosinophilia (> 5%).

If an ECG abnormality develops during the course of the study that meets the following criteria, the subject should be withdrawn:

- Any QTc interval > 500 milliseconds, correction by Fridericia's formula;
- Any QTc interval increase from baseline > 60 milliseconds, correction by Fridericia's formula;
- New onset of arrhythmias such as ventricular tachycardia, multifocal ectopic tachycardia, ventricular triplets, supraventricular tachycardia, atrial fibrillation, second- or third-degree heart block, or bradyarrhythmias; or
- New onset of ECG signs of cardiac ischemia such as, but not limited to, ST segment abnormalities (elevation or depression).

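### SAP 6.3 can leave repeat and off-schedule liver values out of the by-visit tables, and SAP 9.4 plans no count of subjects at the protocol's ULN multiples

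*SAP*

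**What the plan says.** SAP 6.3 maps unscheduled and early-termination visits to windows by study day and flags one record per window for analysis. The order of choice is: "If there is a scheduled visit/week for the analysis visit window, then the scheduled visit/week data will be used"; failing that, "If there is no scheduled visit/week for the analysis visit window, the data closest to the scheduled day will be used", with the later record taken in a tie. Records not chosen "will also be listed in subject listings". No exception is made for safety laboratory data. The post-dose windows in SAP Table 2 are Days 2–42 (Visit 3, target Day 28), 43–70 (Visit 4), 71–84 (Visit 5) and 85–86 (end-of-study contact). There is none after Day 86.

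SAP 9.4 summarises observed values and change from baseline by arm and time point. The default statistics in SAP 6.1 include the maximum. SAP 9.4 also states that "normal ranges for each parameter will be used to categorize the test result as low", normal or high, with counts over time and shifts from baseline.

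Protocol 9.3.6 sets the sampling: "Clinical chemistry (CMP) will be assessed on Visits 1 (Screening Visit), 2, 3, and 5". It adds that "blood may be drawn on Visit 4 and/or the End-of-Study Call/Visit as dictated by occurrence of subject symptom or adverse events". Protocol 9.3.13 requires confirmation: "An increase in serum aminotransferases to > 3x ULN will be followed by repeat testing within 48 to 72 hours". Its withdrawal criteria are ALT or AST above 8x ULN, above 5x for more than two weeks, or above 3x with raised bilirubin (above 2x ULN), raised INR or listed symptoms. Its study-level trigger includes persistent AST or ALT elevation above 3x ULN in 5% of enrolled subjects, with a repeat test given as the example of persistence.

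**The concern.** Safety and tolerability is a secondary objective (Protocol 4.2), and raised transaminases are a named risk of the active ingredient (Protocol 8.4.1.1). The protocol judges that risk by multiples of ULN and by confirmation on repeat. The SAP's laboratory tables do neither: they classify against the normal range, and the record rule can put the confirming or peak value in a listing.

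The ECG section shows the gap. SAP 9.6 counts subjects with QTcF increases above 60 msec and values above 500 msec, which are cut-offs that Protocol 9.3.13 also uses. The liver criteria in the same protocol section have no such table. At stake is whether the study report can state, per arm, how many subjects passed each liver threshold at any time after dosing.

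**Working it through.** The plan states no figure on this point, so there is none to reproduce. The check places possible draw days in the windows of SAP Table 2.

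**Inputs.** Windows are from SAP Table 2. On-treatment scheduled chemistry is at Visits 3 and 5 only (Protocol 9.3.6). Visit 3 is Day 28 ± 5 and Visit 5 is Day 84 ± 5 (Protocol Table 1). The repeat comes 2 to 3 days later (Protocol 9.3.13).

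**1. Off-schedule draw on Days 2–84.** Assume that the Visit 3 sample exists, that the Visit 5 sample was taken by Day 84, and that SAP 6.3 is applied per parameter.
- Days 2–42: 42 − 2 + 1 = 41 days, scheduled chemistry present, draw displaced.
- Days 43–70: 70 − 43 + 1 = 28 days, no scheduled chemistry, draw can be the Day 56 record.
- Days 71–84: 84 − 71 + 1 = 14 days, scheduled chemistry present, draw displaced.
- Displaced: (41 + 14) / 83 = 55/83 = 66%. Kept: 28/83 = 34%.

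These are shares of calendar days, not of expected draws. If *scheduled visit* instead means the visit itself, an attended Visit 4 without chemistry could block the 28 days too. The range is therefore 55 to 83 of 83 days, leaving aside a draw made at Visit 4 itself.

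**2. Repeat after Visit 3.** The visit falls on one of 11 days (Days 23–33), and with 2 lags there are 22 combinations. The repeat falls on Days 25–36, always inside Days 2–42. Displaced: 22 of 22.

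**3. Repeat after Visit 5.** The visit falls on Days 79–89, again giving 22 combinations.
- Repeat by Day 84, beside the scheduled sample: 7 of 22, displaced.
- Repeat on Day 85 or 86, no scheduled chemistry: 4 of 22, can be tabulated.
- Repeat after Day 86, no window: 11 of 22.

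**4. Early termination.** A draw after Visit 3 and up to Day 42 loses to the Visit 3 record. Where the scheduled draw was missed, the early-termination or unscheduled record closest to the target day is used, whether or not it is the worst.

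**5. Illustrations (hypothetical).**
- ALT is 3.2x ULN on Day 28 and 8.5x on Day 31. The Visit 3 tables use 3.2x: it enters the mean, the maximum, the high count and the shift. The 8.5x value is in a listing.
- ALT is 6x ULN on an unscheduled Day 15 draw and normal on Day 28. The Visit 3 tables show normal. This holds only if the subject stays in the trial and gives the Day 28 sample.

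**6. What the laboratory tables can show.** A scheduled value of 3.2x counts as high, as does one of 1.05x. The arm maximum is one number per visit. Where one ULN applies, it shows whether any analysed record passed a threshold, but in general not how many subjects did, and it says nothing about displaced records.

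**The case against.** The strongest reply is that little is hidden. Scheduled values above 3x ULN enter the means, maxima, high counts and shifts. Off-schedule values on Days 43–70 or 85–86, or where the scheduled draw was missed, can be tabulated. Withdrawn subjects appear in the disposition table (SAP 7.1). Abnormal laboratory findings can be adverse events (Protocol 9.3.11.1), and SAP 9.3 tabulates all, serious and withdrawal-related events by arm. Potential Hy's Law cases are handled as suspected unexpected serious adverse reactions. The blinded liver reviews in Protocol 9.3.13 are not governed by SAP 6.3. Every displaced value is still listed.

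All of this is correct, and it limits the point. It does not replace the missing table. Event tables depend on investigator reporting and are organised by preferred term. Disposition gives a reason, not a ULN multiple. Listings give no count by arm.

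Three stronger inferences are not supported:
- **That off-schedule values or cases above 3x ULN cannot reach any safety table.** The routes above show that they can.
- **That the rule makes every by-visit liver summary look cleaner.** A repeat follows an elevated value, and after Visit 3 that scheduled value stays in the table; if the repeat is lower, the higher value is the one shown. What is certain is narrower: the worst value among selected records cannot exceed the worst among all records.
- **That one missed case would matter against the protocol's lovastatin figure.** The protocol reports that "persistent increases (to more than 3 times the upper limit of normal) in serum transaminases occurred in 1.9% of adult patients", but these patients were treated for at least one year, with increases usually appearing at 3 to 12 months. That is no benchmark for 12 weeks of dosing.

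**Conclusion.** The point holds as a gap in the safety tables. Under the stated record rule, repeat, symptom-prompted and early-termination liver values are left out of the by-visit tables wherever the Visit 3 or Visit 5 window also holds the scheduled sample. Repeats after Day 86 belong to no window. Separately, no planned laboratory table counts subjects by worst post-dose value or at the protocol's ULN multiples, and none shows persistence.

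The size is 55 of 83 treatment days and all 22 repeat-day combinations after Visit 3. After Visit 5, 7 of 22 are displaced and 11 of 22 have no window. The day count assumes that both scheduled samples exist, with Visit 5 by Day 84, and that the rule works per parameter. The documents give no expected number of such draws, so the number of affected subjects cannot be estimated.

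The SAP is based on protocol version 3.0 and the current protocol is version 8.0. Whether the liver criteria stood in version 3.0 cannot be checked. This is a worthwhile, nearly free improvement; it does not affect the efficacy conclusions.

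**What to change.** - **SAP 9.4:** add one by-arm table of the worst post-dose ALT, AST and total bilirubin per subject over all records: scheduled, repeat, unscheduled, early termination and after Day 86. Give n (%) with ALT or AST above 3x, 5x and 8x ULN; bilirubin above 2x ULN; and ALT or AST above 3x with bilirubin above 2x ULN. State whether that combination must come from the same sample. The denominator is subjects with at least one post-dose value of the tests concerned.
- **SAP 6.3:** state that window selection governs by-visit summaries only, and whether it is applied per parameter or per visit.
- **Windows:** reconcile the protocol's Visit 5 range (Days 79–89) with SAP Table 2, where the Visit 5 window ends at Day 84 and the last window at Day 86.

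The cut-offs are the protocol's own and are used only for tabulation; no clinical rule changes. The cost is SAP wording and one extra descriptive table, with no new data, visits or patients.
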